## 8. SAFETY ANALYSIS

Safety evaluations will be based on exposure and compliance to study drugs, the incidence, severity, attribution and type of AEs, and changes in the patient's vital signs, and clinical laboratory results.

### 8.1 Trial drug Exposure and Compliance

Extent of treatment exposure to SNS-301, will be assessed for each of the two study stages.

- Duration of SNS-301 treatment (week), will be calculated as: (Last dose date – first dose date + 1) / 7
- Was full dose of SNS-301 administered? (Yes/No)
- Were any injection or device malfunctions noted? (Yes/No)
- Type of Malfunction (Device failed, User Error)
- Did the malfunction affect the dose received by the subject? (Yes/No)

Pembrolizumab exposure will be summarized by the following parameters:

- Duration of Pembrolizumab treatment (week), calculated as: (Last dose date – first dose date + 1) / 7
- Was full dose of Pembrolizumab administered? (Yes/No)
- Was infusion interrupted? (Yes/No)

Sponsor: Sensi Biotherapeutics

Protocol: SNS301-2-2

- Reason for interruption (AE, IV Issue Other)

## 8.2 Dose-Limiting Toxicities

Dose-Limiting Toxicities (DLTs) are events identified below that must be reported in an expeditious manner. DLTs may or may not be serious adverse events as an Unexpected Adverse Event (SUSAR). DLTs are assessed up to week 6 for patients enrolled in the Safety Run-In period.

- 1) Grade 4 non-hematological toxicities (excluding alopecia) of any duration
- 2) Grade 3 non-hematologic (non-laboratory) toxicity lasting > 3 days despite optimal supportive care
- 3) Any Grade 3 or Grade 4 non-hematologic laboratory value if: a). medical intervention is required to treat the patient; b), the abnormality leads to hospitalization; c). The abnormality persists for >1 week.
- 4) Grade 4 hematologic toxicity, other than those specified in criteria 5 and 6 below, lasting > 7 days
- 5) Grade 3 or Grade 4 febrile neutropenia of any duration
- 6) Grade 3 thrombocytopenia in combination with a grade 3 or greater blood and lymphatic system disorder
- 7) Grade 3 AST or ALT that is associated with a grade 2 rise in bilirubin

Safety analysis will be based on the safety analysis set.

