If an investigator receives an IND safety report or other specific safety information (e.g., SUSAR, summary or listing of SAEs) from the sponsor, the investigator will review and file along with the Investigator's Brochure and will notify the IRB/IEC, if appropriate according to local regulations. In these instances, the ICF may need to be revised to inform the patient of any new safety concern.

9.3.7 *Unanticipated (Serious) Adverse Device Effect (UADE)*

A UADE is any serious adverse effect on health or safety or any life-threatening problem or death caused by, or associated with, a device, if that effect, problem, or death was not previously identified in nature, severity, or degree of incidence in the investigational plan or application (including a supplementary plan or application), or any other unanticipated serious problem associated with a device that relates to the rights, safety, or welfare of patients.

Per the definition above, a UADE is a type of SAE that requires expedited reporting on the part of the Sponsor. As a reminder, all SAEs regardless of relationship to device, drug or procedure are to be reported to Sponsor by the trial Investigator within 24 hours. Sponsor will assess each device related SAE to determine if anticipated based on prior identification within the investigational plan. The Sponsor may notify a regulatory authority within the time frame specified by local requirements but no later than 10 business days for UADE.

UADE form should be reported to:

Global Safety and Pharmacovigilance, Advanced Clinical

Email: [contact]

9.3.8 *Dose-Limiting Toxicities*

DLTs are events [toxicities] specifically identified in this protocol that must be reported in an expeditious manner. Information regarding DLTs should be recorded on a DLT Confirmation Worksheet and faxed or emailed within 24 hours of site personnel becoming aware of the event. DLTs may or may not be serious adverse events as an Unexpected Adverse Event. DLTs are assessed up to week 6 for patients enrolled in the Safety Run-In period.

Any of the following, if judged to be associated with SNS-301 (i.e., possibly related, probably related, or related to), will be considered a DLT which are based on the NCI-CTCAE V5.0 criteria:

- 1) Grade 4 non-hematological toxicities (excluding alopecia) of any duration
- 2) Grade 3 non-hematologic (non-laboratory) toxicity lasting > 3 days despite optimal supportive care

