Safety evaluations will be based on the incidence, severity, attribution and type of AEs, and changes in the patient's vital signs, and clinical laboratory results, analyzed using the safety analysis set.

Summarization of toxicity data will focus on incidence of treatment-emergent adverse events. Treatment-emergent adverse events are defined as any AE that occurs during or after administration of the first dose of treatment through 30 days after the last dose, any event that is considered study drug-related regardless of the start date of the event, or any event that is present at baseline but worsens in intensity. The incidence of serious adverse events, adverse events, drug-related adverse events, and adverse events leading to discontinuation or death will be presented in tabular form by system organ class and preferred term. Adverse events will be assessed for severity according to the NCI CTCAE, version 5.0.

A presentation of dose-limiting toxicities among patients in the safety run-in set will be presented.

Other safety evaluations including vital sign, laboratory and physical exam results will be presented over time.

10.4.4 *Other Analyses*

Antigen-specific cellular immune response assessed by but not limited to Interferon- γ secreting T lymphocytes will be summarized by visit. Immune related gene expression will be evaluated with pre- and post-treatment tissue biopsies. Cytokine and chemokine profiles will be summarized by visit.

Additional exploratory analyses may be performed, including evaluation of relationship between efficacy endpoints and immunology parameters.

10.4.4.1 *Pharmacodynamics*

Exploratory pharmacodynamic (PD) analysis will be performed using dose, vaccine-specific antibody response (geometric mean titer), antigen-specific T and B cell indices, and the relative expression of ASPH in each patient's tumor. The PD will be balanced and optimized to the degree of antigen-specific immune response and minimized for the production of regulatory immune processes.

10.5 *Interim Analyses*

For each cohort, the objective response rate will be assessed at the completion of stage 1 of the 2-stage design, after 15 patients complete the 12-week follow-up period or discontinue prior due to disease progression. See Section 10.2 for additional details.

10.5.1 *Safety Committee*

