## 4. ANALYSIS POPULATIONS

### *Safety Analysis Set*

The Safety Analysis Set comprises all patients who receive at least 1 dose of the study treatment or component of the study treatment.

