### *Safety Run-In Set*

Safety Run-in Set comprises all patients who receive at least 1 dose of the study treatment or component of the study treatment as part of the safety run-in.

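### SAP 8.2 restates the DLT criteria without the SNS-301 attribution condition, and the SAP assigns no analysis set to the DLT outputs

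*SAP*

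**What the plan says.** Protocol 9.3.8 makes attribution part of the DLT definition: "Any of the following, if judged to be associated with SNS-301 (i.e., possibly related, probably related, or related to), will be considered a DLT". Seven criteria follow. Sites record each DLT on a DLT Confirmation Worksheet.

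Protocol 10.4.3 uses two populations. General safety (adverse events, vital signs and "clinical laboratory results, analyzed using the safety analysis set") goes on all treated patients. DLTs are handled separately: "A presentation of dose-limiting toxicities among patients in the safety run-in set will be presented".

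SAP 8.2 opens with "Dose-Limiting Toxicities (DLTs) are events identified below that must be reported in an expeditious manner" and lists the same seven criteria with no attribution condition. It keeps the protocol's time and patient limit: "DLTs are assessed up to week 6 for patients enrolled in the Safety Run-In period". It closes with "Safety analysis will be based on the safety analysis set".

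SAP Section 4 defines both sets. The Safety Run-In Set covers patients dosed with any "component of the study treatment as part of the safety run-in". For the wider set, "The Safety Analysis Set comprises all patients who receive at least 1 dose of the study treatment" or a component of it. SAP Section 5 counts the run-in set in the disposition table. SAP 8.3 includes DLTs in the overall adverse event summary, in the tables by system organ class and preferred term, and in a listing, and names no set for any of them.

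**The concern.** SAP 8.2 reads as a self-contained definition, because it says that DLTs are the events it goes on to list. Anyone programming from it would apply the grade and duration criteria and never ask about SNS-301. That matters in a two-drug trial in advanced cancer. A sufficiently long Grade 3 event attributed only to pembrolizumab, or only to the disease, meets the SAP list but is not a DLT under the protocol. SAP 8.3 itself tabulates SNS-301-related and pembrolizumab-related events separately, so the distinction is meant to be available.

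The denominator has a similar gap. The protocol's instruction to use the Safety Run-In Set did not reach the SAP, and the one set named in the DLT section is the much larger one. SAP Section 1 says that the document sets out its differences from the protocol's analysis methods. Neither difference is set out, so both look like omissions and not decisions.

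At stake is the DLT result as it appears in the study report. Extra events would inflate the numerator, and patients never assessed for DLT would dilute the denominator.

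**Working it through.** The plan states no DLT rate, so there is no figure to reproduce. The check compares the texts and then sizes the two gaps.

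**1. Texts side by side**

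| Element | Protocol 9.3.8 and 10.4.3 | SAP 8.2 and 8.3 |
|---|---|---|
| Seven criteria | Listed | Listed, same content |
| Judged associated with SNS-301 | Required | Absent; not restored elsewhere |
| Run-in patients, to Week 6 | Yes | Yes |
| Set for DLT outputs | Safety Run-In Set | Not assigned |
| Set for general safety | Safety Analysis Set | Safety Analysis Set |
| Source of DLT records | DLT Confirmation Worksheet | Not stated |

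Two elements are lost (attribution and the set for DLT outputs), and the data source is left open.

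**2. Denominator**

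Inputs: a run-in of up to 6 patients (Protocol 5.2, SAP 2.2); up to about 30 patients per cohort and about 60 in all (same sections); summaries by cohort and overall (SAP 3.1). If a DLT occurs before the first three patients complete Week 6, all six must be followed to Week 6, so 6 is the natural denominator in that case.

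Rate = patients with a DLT / patients in the set.

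- One DLT: 1/6 = 16.7%; 1/30 = 3.3%; 1/60 = 1.7%.
- Two DLTs: 2/6 = 33.3%; 2/30 = 6.7%; 2/60 = 3.3%.

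The understatement is 30/6 = 5-fold by cohort and 60/6 = 10-fold overall. These are planned maxima. If a cohort does not expand, the dilution is smaller.

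**3. Numerator**

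With the run-in denominator of 6, each additional patient wrongly counted adds 1/6 = 16.7 points. With 60 it adds 1/60 = 1.7 points. A second event in a patient already counted adds nothing. The two gaps push in opposite directions, so their sizes should not be quoted together on different denominators. For example, with one true DLT patient and one patient with an unrelated qualifying event, the protocol result is 1/6 = 16.7%. Dropping attribution alone gives 2/6 = 33.3%. Dropping attribution and using all treated patients gives 2/60 = 3.3%.

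The documents give no rate for unrelated qualifying events, so the following is assumption only. Let p be the chance that a patient has an SNS-301-related DLT and q the chance of an unrelated qualifying event, independent of each other and between patients. Then t = 1 - (1 - p)(1 - q), and the chance that at least 2 of 6 patients are counted is 1 - (1 - t)^6 - 6t(1 - t)^5.

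| p | q = 0% | q = 5% | q = 10% | q = 20% |
|---|---|---|---|---|
| 5% | 3.3% | 10.9% | 21.2% | 44.2% |
| 10% | 11.4% | 21.2% | 32.0% | 53.6% |

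These are chances of what a table derived from SAP 8.2 alone would show. They are not chances of stopping enrollment, which the protocol definition governs.

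**4. What the trial had shown**

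Protocol 3.1.2 reports 11 patients enrolled at 29 October 2020, three treatment-related Grade 3 events in 2 patients, and no DLTs. Grade 3 events therefore do occur. Their duration, timing and attribution to one drug or the other are not given, so it cannot be said that any would be reclassified under the SAP list.

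**The case against.** A reader might infer that the SAP has moved the DLT analysis to the Safety Analysis Set. The text does not say so. The closing sentence of 8.2 concerns safety analysis in general and matches the protocol's own general rule in 10.4.3. The same section confines DLT assessment to run-in patients through Week 6, so the patients who can enter the numerator are already limited. What is open is the denominator. This objection stands.

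A reader might also infer that the DLT table is bound to be wrong. That does not follow either. Sites report DLTs on a dedicated worksheet under the protocol definition, and several criteria, such as whether supportive care was optimal, need clinical judgement that a program cannot supply. A table built from the worksheets would carry the attribution. The SAP is also expressly based on protocol Version 4.0, and nothing suggests an intention to redefine DLTs. This stands in part: the SAP names no data source, so the safeguard exists in the protocol but is not tied to the output.

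Third, the run-in rule in Protocol 5.2 is a count (none, one, or two or more) applied under the protocol, and neither document makes a DLT rate an estimand. With no DLTs at the October 2020 cutoff, before the SAP was finalised in 2021, the run-in decision may already have been taken. If the count stays at zero, every denominator gives 0%. The planned DLT listing would also expose a misclassified event. All of this limits the consequence. It does not make the SAP rule agree with the protocol.

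**Conclusion.** The point holds as a mismatch between SAP and protocol. SAP 8.2 omits the attribution condition of Protocol 9.3.8, and the SAP does not carry over the Protocol 10.4.3 instruction to present DLTs in the Safety Run-In Set. The DLT result could be misderived: in the numerator if DLTs were derived from SAP 8.2 alone, and in the denominator if all treated patients were used.

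The denominator effect for one DLT is 16.7% against 3.3% (by cohort) or 1.7% (overall). It assumes a full six-patient run-in and both cohorts at planned maximum size. The numerator effect cannot be sized from the documents, and the range shown rests on assumed event rates.

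It would go too far to conclude that run-in safety decisions are compromised. Those follow the protocol definition, so the harm is confined to the reported result. The omission is still worth correcting, because the SAP states a definition that differs from the protocol's and the correction is cheap.

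**What to change.** In the SAP:

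- In 8.2, restore the attribution condition by cross-reference to Protocol 9.3.8 instead of rewording it.
- Add a sentence assigning all DLT outputs in 8.2 and 8.3 to the Safety Run-In Set.
- Keep the general sentence on the Safety Analysis Set but move it to the opening of Section 8. It is the only statement in that section of the population for adverse events, laboratory and other safety analyses, so deleting it would leave them without one.
- State that DLTs are taken from the DLT Confirmation Worksheet.

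Separately, Protocol 9.3.8 describes association in three graded terms (possibly, probably, related), while Protocol 9.3.3.2 and SAP 8.3 record causality only as Related or Not Related. The sponsor should reconcile these passages. Which wording is right is a clinical decision and is not proposed here.

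The cost is a few sentences in the SAP and a short protocol clarification. No new data are needed, and the design and sample size do not change.

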## 8.3 Adverse Events

### Adverse event (AE)

is defined as any untoward medical occurrence associated with the use of a drug in humans, whether or not considered drug related. Any AE that occurs prior to the first dose is part of the medical history. AEs will be collected from the time of informed consent until 30 days after the last dose of study treatment or until initiation of another anti-cancer therapy, whichever occurs first.

Adverse events (AEs) will be coded using MedDRA v20 or later and will be classified by System Organ Class (SOC) and preferred term (PT).

Treatment-emergent adverse events (TEAEs) are defined as any AE that occurs during or after administration of the first dose of treatment through 30 days after the last dose, any event that is considered study drug-related regardless of the start date of the event, or any event that is present at baseline but worsens in intensity.

Severity of AEs will be assessed according to CTCAE (v5.0):

Sponsor: Sensi Biotherapeutics

Protocol: SNS301-2-2

- Grade 1: Mild; asymptomatic or mild symptoms; clinical or diagnostic observations only; intervention not indicated.
- Grade 2: Moderate; minimal, local or noninvasive intervention indicated; limiting age- appropriate instrumental ADL.
- Grade 3: Severe or medically significant but not immediately life-threatening; hospitalization or prolongation of hospitalization indicated; disabling; limiting self-care ADL.
- Grade 4: Life-threatening consequences; urgent intervention indicated.
- Grade 5: Death related to AE. (Grade 5 (Death) may not appropriate for some AEs and therefore may not an option.)

Prior AEs are those occurring after subject sign off the informed consent and before the administration of the first dose of study treatment.

Relationship to study medication is categorized as follows based on clinical decision using all available information at the time of completing the CRF:

- Related (The AE could medically (pharmacologically/clinically) be attributed to the study drug under investigation in this clinical study protocol)
- Not related (The AE could not medically (pharmacologically/clinically) be attributed to the study drug under investigation in this clinical study protocol.)

Systemic administration site reactions will be considered as Adverse Events of Special Interest (AESI). The area around the administration site will be assessed by a medically qualified individual for adverse reactions at least 30 minutes post study drug administration. The Investigator will grade any ASRs according to the NCI-CTCAE V5.0 (excluding the actual expected micro-injection punctures).

An unanticipated (serious) Adverse Device Effect (UADE) is any serious adverse effect on health or safety or any life-threatening problem or death caused by, or associated with, a device, if that effect, problem, or death was not previously identified in nature, severity, or degree of incidence in the investigational plan or application (including a supplementary plan or application), or any other unanticipated serious problem associated with a device that relates to the rights, safety, or welfare of patients.

An overall AE summary for number of subjects will be presented for the following categories:

- Any Adverse Event
- Any Treatment-Emergent Adverse Event (TEAE)
- Any deaths within the AE reporting period

Sponsor: Sensi Biotherapeutics

Protocol: SNS301-2-2

- Any study drug-related adverse event (TRAЕ) (i.e. related to SNS-301 or Pembrolizumab)
- Any SNS-301-related adverse event (TRAЕ)
- Any Pembrolizumab-related adverse event (TRAЕ)
- Any AE related to device for injection
- Any AE related to a Dose-Limiting Toxicity (DLT)
- Any TEAE  $\geq$  CTCAE Grade 3
- Any TRAE  $\geq$  CTCAE Grade 3
- Any treatment-emergent Serious AEs (SAEs)
- Any Serious TRAEs
- Any TEAE leading to treatment (SNS-301 or Pembrolizumab) discontinuation
- Any TEAE leading to SNS-301 treatment discontinuation
- Any TEAE leading to Pembrolizumab treatment discontinuation
- AESIs
- UADEs

The following events will be tabulated by SOC and PT. Summaries will be sorted by decreasing frequency of PT within SOC which is sorted alphabetically.

- TEAEs by SOC and PT
- TEAEs by PT frequency only
- Treatment-emergent SAEs
- SNS-301 Treatment-related AEs
- Pembrolizumab Treatment-related AEs
- SNS-301 Treatment-related SAEs
- Pembrolizumab Treatment-related SAEs
- TEAEs leading to SNS-301 treatment discontinuation or death
- TEAEs leading to Pembrolizumab treatment discontinuation or death
- DLTs
- AESIs

Sponsor: Sensi Biotherapeutics

Protocol: SNS301-2-2

A summary of TEAEs by SOC, PT and maximum severity, sorted by decreasing frequency of PT within SOC which is sorted alphabetically, will also be provided for:

- All TEAEs
- TEAEs  $\geq$  CTCAE Grade 3
- SNS-301 Treatment-related AEs
- Pembrolizumab Treatment-related AEs
- TRAEs  $\geq$  CTCAE Grade 3

In tabulation by severity grade, only the most severe SOC for each subject will be included for a given SOC. For a given PT, only the most severe PT for each subject will be included.

The following listings will be provided:

- All AEs
- DLTs
- SAEs
- AESIs
- TEAEs leading to study treatment discontinuation
- Deaths in the AE reporting period

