In order to be eligible for participation in this trial, the patient must:

1. Provide signed IRB approved informed consent in accordance with institutional guidelines.
2. Be 18 years of age or older on the day of signing the informed consent, and able and willing to comply with all trial procedures.
3. Have histologically or cytologically documented locally advanced unresectable or metastatic/recurrent SCCHN and meet the criteria of either Cohort A or B.

Cohort A: Patients with Ongoing CPI Therapy

- a. Patients currently receiving a checkpoint inhibitor (CPI; anti-PD-1 and anti-PD-L1 agents).
- b. Patients currently receiving a CPI must be considered by Investigator to have the potential to derive clinical benefit from continued treatment with pembrolizumab.
- c. Based on RECIST 1.1/iRECIST criteria on current CPI treatment (prior to initiation of this study), patients must have a best response of stable disease (SD) or first evidence of progressive disease (PD) after a minimum of 12 weeks of a CPI.
- d. Patients on other CPI therapy than pembrolizumab must be willing to switch over to pembrolizumab therapy.

Cohort B: Patients without Previous CPI Therapy

- a. Patients must be checkpoint inhibitor naïve (anti-PD-1 and anti-PD-L1 agents)
- b. Patients should receive study treatment as first line (PD-L1 positive) or as second line (PD-L1 negative) systemic therapy in the advanced/metastatic setting.
4. Have measurable disease, as defined by RECIST version 1.1 (investigator assessment).
5. Have a performance status of 0 or 1 on Eastern Cooperative Oncology Group (ECOG) Performance Scale.
6. Have a life expectancy of ≥ 3 months.

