9.3 Adverse Events and Serious Adverse Events

9.3.1 *Definition of Adverse Event (AE)*

Adverse event is defined as any untoward medical occurrence associated with the use of a drug in humans, whether or not considered drug related. Any AE that occurs prior to the first dose is part of the medical history. AEs will be collected from the time of informed consent until 30 days after the last dose of study treatment or until initiation of another anti-cancer therapy, whichever occurs first.

Abnormal laboratory values should not be listed as separate AEs if they are considered to be part of the clinical syndrome that is being reported as an AE unless worsened on study treatment. It is the responsibility of the Investigator to review all laboratory findings in all patients and determine if they constitute an AE. Medical and scientific judgment should be exercised in deciding whether an isolated laboratory abnormality should be classified as an AE. Any laboratory abnormality (grade 1 and greater that are listed in the NCI-CTCAE V5.0) considered to constitute an AE should be reported on the Adverse Event CRF.

Pre-planned procedures (surgeries or therapies) that were scheduled prior to the start of study drug exposure are not considered AEs. However, if a pre-planned procedure is performed earlier than anticipated (e.g., as an emergency) due to a worsening of the pre-existing condition, the worsening of the condition should be captured as an AE.

Progression of the cancer under trial is not considered an adverse event unless it is considered to be drug related by the investigator. Patients will be encouraged to spontaneously report any AE. Patients will be questioned and/or examined by the Investigator and his/her medically qualified designee for evidence of AEs. The questioning of study patients with regard to the possible occurrence of AEs will be generalized, such as, "How have you been feeling since your last visit?" Information gathering for AEs should generally not begin with direct solicitation from patients regarding the presence or absence of specific AEs. Study personnel will ask open-ended questions to obtain information about AEs at every visit. Date and time of onset and resolution (if applicable) of the AE will be documented in the patient's clinical notes.

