Any medical condition that begins after obtaining informed consent will be recorded the AE section of the CRF. If the patient's condition worsens during the study, the event will be recorded as an AE.

All AEs/SAEs will be captured on the appropriate case report form. Information to be collected includes event description, date of onset, severity, relationship to study intervention and date of resolution.

10. Statistical Considerations

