## 9. STATISTICAL/ANALYTICAL ISSUES

### 9.1 Handling of Dropouts or Missing Data

All available data will be presented on the data listings as collected.

Algorithms for imputing partial or missing dates related to AEs and prior/concomitant medications are shown below.

Table 3      Imputation Rules for Partially Missing Dates

Variable	Missing Day	Missing Day, Month	Missing Day, Month, Year
Date of Last Therapy/Date of Initial Diagnosis	Assign 1	Assign January 1 if prior to date of informed consent, otherwise use date of informed consent	Missing (do not impute)
Adverse Event/Medication Start Date	Assign first day of month unless it is the month of first dose of study medication. Otherwise, assign date of first dose of study medication.	Assign January 1 unless the year is year of first dose of study medication Otherwise, assign date of first dose of study medication.	Assign date first dose of study medication.
Adverse Event/Medication End Date	Assign the last day of the month or end of study date, whichever is earlier.	Assign December 31 or end of study date, whichever is earlier.	If ongoing, end date is missing. Otherwise, assign end of study date.

Every effort to re-contact the patient lost to follow-up patients will be made, to identify the reason why he/she failed to attend the visit, and to determine his/her health status, including at least his/her vital status. Data from lost to follow-up subjects to the date of last recorded contact will be included in the analyses.

Non-evaluable patients will be replaced.

Sponsor: Sensi Biotherapeutics

Protocol: SNS301-2-2

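### The treatment-emergent AE definition has no lower date limit for drug-related events, and the start-date imputation ignores the end date, so some pre-dose events can be counted as treatment-emergent

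*SAP*

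**What the plan says.** SAP 8.3 and Protocol 10.4.3 define a treatment-emergent event by three alternative limbs: onset from first dose to 30 days after the last dose; "any event that is considered study drug-related regardless of the start date of the event"; or presence at baseline with later worsening. The second limb has neither a lower nor an upper date limit.

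SAP 8.3 says three other things about the period before dosing:
- On collection: "AEs will be collected from the time of informed consent until 30 days after the last dose of study treatment" (or until another anti-cancer therapy starts, if sooner).
- On pre-dose events, in wording that Protocol 9.3.1 shares: "Any AE that occurs prior to the first dose is part of the medical history".
- On the same interval again: "Prior AEs are those occurring after subject sign off the informed consent and before the administration of the first dose of study treatment".

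Protocol 9.3.13 adds: "Any medical condition that begins after obtaining informed consent will be recorded the AE section of the CRF". Neither document says which statement takes precedence.

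For relatedness, the combined row of the SAP's AE summary covers events "i.e. related to SNS-301 or Pembrolizumab", and Protocol 7.1.1.2 defines study treatment as both agents. Under the inclusion criteria, Cohort A patients are on an anti-PD-1 or anti-PD-L1 agent at entry, with at least 12 weeks of it behind them.

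For an AE start date with the day missing, SAP 9.1, Table 3 reads: "Assign first day of month unless it is the month of first dose of study medication. Otherwise, assign date of first dose of study medication". The same logic applies to the year when day and month are both missing. A wholly missing start date becomes the first-dose date. No comparison with the AE end date is stated.

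**The concern.** Safety is the first primary objective and the trial has no control arm, so the TEAE and treatment-related tables carry the safety conclusion by themselves. A treatment-emergent flag is meant to separate what began or worsened under study treatment from what was already there. Two rules weaken that separation.

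The first is the undated related limb. In most trials it does little harm before dosing, because nothing can be related to a drug not yet given. Cohort A differs: a patient may have been taking one of the two study drugs for months when consent is signed.

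The second is the imputation rule, which does not depend on relatedness or cohort. It can place the start of an event after its recorded end.

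The conflicting labels for the interval from consent to first dose add a practical problem. Two programmers following the plan faithfully could put the same event in the medical history table, among the Prior AEs, or in the TEAE tables.

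**Working it through.** The plan states no figure on this point, so there is none to reproduce. The check applies the rules as written.

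**1. Related limb.** Take a Cohort A patient already on pembrolizumab who consents on Day -20 and has a rash on Day -10 that the investigator attributes to pembrolizumab.
- Collected as an AE? Yes: onset is after consent, and the consent window runs to 28 days before Day 0 (Protocol Table 1, footnote a; SAP Appendix A, footnote a).
- First TEAE limb? No: onset precedes first dose.
- Second limb? Yes: it is related to a study drug and the limb ignores onset.
- Rows entered: TEAE, pembrolizumab-related, and combined treatment-related. The treatment-related rows in SAP 8.3 have no onset limit of their own.
- Rows not entered: SNS-301-related, which SAP 8.3 tabulates separately.
- Other labels for the same event: medical history and Prior AE, both from SAP 8.3. No table or listing is assigned specifically to Prior AEs.

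**2. Table 3.** Suppose first dose is 15 March 2021.

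| Recorded start | Imputed start | Moved to first dose? |
|---|---|---|
| 5 March 2021 | 5 March 2021 | No |
| March 2021 | 15 March 2021 | Yes |
| February 2021 | 1 February 2021 | No |
| 2021 | 15 March 2021 | Yes |
| 2020 | 1 January 2020 | No |
| wholly missing | 15 March 2021 | Yes |

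If the event recorded as starting in March has a known end date of 10 March, its imputed start falls five days after its end, and it meets the first TEAE limb.

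**3. How often the rule moves a truly pre-dose onset.** Assumptions, not from the documents: first-dose dates spread evenly over 2021, and onset uniform over the stated interval.

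| Start date recorded | Onset Day -28 to -1 | Onset Day -84 to -1 |
|---|---|---|
| Complete | 0% | 0% |
| Day missing | 52% | 18% |
| Day and month missing | 96% | 88% |
| Wholly missing | 100% | 100% |

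These are shares within each type of incomplete date. The documents do not say how many AE dates will be incomplete, so they do not convert to a number of events.

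**4. Size per affected patient.**
- A specific-term or related-AE row, if the patient is not already counted there: 1/30 = 3.3 points for a full cohort; 1/15 = 6.7 points for a stage 1 cohort.
- Overall TEAE incidence: the patient adds to it only if he or she has no other TEAE. Protocol 3.1.2 reports TEAEs in 9 of 11 patients (82%), leaving 2/11 = 18% without one. If misclassification is independent of having another TEAE (assumption), the expected addition is 2/11 × 3.3 = 0.6 points at n=30 and 2/11 × 6.7 = 1.2 points at n=15.

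**The case against.** The strongest reply is that the exposure is narrow. Relatedness is an investigator's judgement about the drug under study in this protocol, and the factors listed in Protocol 9.3.3.2 are written around SNS-301. Few investigators may mark an event before any on-study dose as related. Not every Cohort A patient arrives on pembrolizumab; other agents are allowed and switched at entry, and no proportion is given. The undated limb also has a proper use: it captures related events that surface after the 30-day window. Assigning an unknown onset to first dose is a common and conservative safety convention. All of this stands and limits the size of the problem. None of it supplies the missing lower bound or end-date check.

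Four stronger readings are tempting, and the documents do not support them:
- **That toxicity from prior checkpoint therapy is generally reported as treatment-emergent.** Collection starts at consent. Earlier events are history and count only if they worsen.
- **That imputation moves pre-dose events as a rule.** Complete dates, and incomplete dates in a known earlier month or year, are never moved. The effect is not specific to Cohort A.
- **That SNS-301-related rates are inflated or pre-dose events vanish.** The two drugs have separate tables, and the plan keeps an any-AE row and listings of all AEs and SAEs.
- **That incidence is overstated by a known amount.** Assuming 1 to 5 affected patients out of 30 gives 3.3 to 16.7 points. That range is a ceiling for one row, and the patient count has no basis in the documents.

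**Conclusion.** The concern holds in this limited form. The related limb of the TEAE definition, in both documents, admits events with onset between consent and first dose when they are judged pembrolizumab-related; in practice this concerns Cohort A patients already on that drug. It contradicts two other sentences in the same SAP section. Independently, Table 3 lets an event known to have ended before dosing be flagged as treatment-emergent, in either cohort.

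The rows at risk are specific preferred terms, pembrolizumab-related and combined treatment-related events, where each affected patient counts for at most 3.3 points at n=30 or 6.7 at n=15. The overall TEAE rate would move less, as most patients are likely to have a TEAE anyway; that rests on the early 9 of 11. The total effect cannot be derived, because the documents give neither the share of Cohort A on pembrolizumab nor the frequency of pre-dose related events or incomplete dates. The rules give a wrong classification as written, and correcting them is cheap, so the change should be made before the tables are programmed.

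**What to change.** 1. **TEAE definition (SAP 8.3 and Protocol 10.4.3).** Limit the related limb to events with onset on or after the first on-study dose. Keep related events that start after the 30-day window. Apply the same lower bound to every treatment-related row and table.
2. **Pre-dose events.** Report events between consent and first dose, including serious ones, only as Prior AEs, in a listing of their own, unless they worsen after first dose. This changes tabulation, not collection or expedited reporting.
3. **Medical-history sentence.** Remove or reconcile it in both Protocol 9.3.1 and SAP 8.3. Changing only one leaves the contradiction in the other.
4. **SAP Table 3.** Impute an AE start to the first-dose date only when the known end date is not before first dose. Never flag as treatment-emergent an event that ended before first dose.

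The cost is a few lines in each document and one programming check. SAP Section 1 already provides for differences from the protocol's analysis methods to be stated there, so the SAP can be corrected first and the protocol aligned at its next amendment. Some TEAE and treatment-related rates may come out slightly lower.
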